7.14 Cohort 4 secondary outcomes

7.14.1 Changes in plasma HIV-1 RNA levels as detected by single copy assay from baseline to after each administration of RMD or placebo in Cohort 4.

NOTE: Only 72hr post-2nd-infusion time point was tested for the primary analysis. Testing of remaining samples is pending on further team discussion.

Included in the analysis of 7.13.1.

7.14.2 Change in cell-associated HIV-1 RNA levels in PBMCs from baseline to after each administration of RMD or placebo in Cohort 4.

NOTE: Only 72hr post-2nd-infusion time point was tested for the primary analysis. Testing of remaining samples is pending on further team discussion.

Included in the analysis of 7.13.2.

7.14.3 Changes in histone acetylation in CD4+ and CD8+ T-cells from baseline to after each administration of RMD or placebo in Cohort 4.

The same analysis approach will be used as in 7.13.2.

7.14.4 Changes in total HIV-1 DNA in PBMCs from baseline to after each administration of RMD or placebo in Cohort 4.

The same analysis approach will be used as in 7.13.2.

Analysis of RNA/DNA ratio will be using the same approach.

7.14.5 Pharmacokinetic parameters for RMD and co-administered antiretroviral drugs (EFV, DTG, or RAL).

Table summarizing of the pharmacologist-estimated PK parameters.

7.14.6 Number/percent of participants in Cohort 4 with HIV-1 RNA levels ≥200 copies/mL at scheduled postinfusion 4 visits.

See 7.7

7.14.7 All reported Grade 2-4 AEs.

List showing all the events with grade 2-4 for each study participant. The list will include the following:

- public ID
- treatment dispensation date
- visit week
- onset date
- resolution date
- event description
- value and units (for laboratory results)
- grade
- 7.14.8 Change in CD4+ T cell percent from baseline to after each administration of RMD or placebo in Cohort4.
- 7.14.9 Changes in the percentage of CD3+ CD4+ and CD3+ CD8+ lymphocytes and cellular markers of immune activation (CD38/HLA-DR or CD69/CD25 expression on CD4+ and CD8+ T-cells) from baseline to after each administration of RMD or placebo in Cohort 4.
- 7.14.10 Change in percentage of total lymphocytes expressing annexin V and/or 7 amino-actinomycin D (7-AAD) from baseline to after each administration of RMD or placebo in Cohort 4.
- 7.14.11 Changes in P-TEFb and HIV-1 expression; changes in PTEF-b phosphorylation in CD4+ and CD8+ Tcells from baseline to after each administration of RMD or placebo in Cohort 4.

For 7.14.8-7.14.11:

Tables:

- Summaries for each outcome at each measurement time point: N, median, 25th and 75th percentiles, min, max
- Summaries for each outcome's absolute change from baseline to each measurement time point: N, median, 25th and 75th percentiles, min, max

Wilcoxon rank sum test will be used for the comparison between groups. Wilcoxon signed rank test will be used to test within-group changes for RMD group.

Time points tested for 7.14.8-7.14.10: pre-entry (-35 to -28 days), pre-entry (-14 to -3 days), 24hr post-1st-infusion, pre-4th infusion, 24hr post-4th-infusion, week 16

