7.11 Cohorts 1-3 secondary outcomes

Unless otherwise specified, these analyses will follow the approach for the primary efficacy outcomes.

7.11.1 Changes in plasma HIV-1 RNA levels as detected by single copy assay from baseline to 6 and 12 hours, and 7, 14, and 28 days after the administration of RMD or placebo.

Included in the analysis of 7.10.1

7.11.2 Change in cell-associated HIV-1 RNA levels in resting CD4+ T-cells from baseline to 14 days after the administration of RMD or placebo.

Included in the analysis of 7.10.2

- 7.11.3 Changes in cell-associated HIV-1 RNA levels in total CD4+ T-cells from baseline to 6, 12, 24 and 48 hours, and 7, 14, and 28 days after completion of RMD or placebo.
- 7.11.4 Changes in histone acetylation in total CD4+ T-cells by flow cytometry from baseline to 12, 24, 48 hours and 7 and 14 days after the administration of RMD or placebo.

NOTE: Mean and median FI records with sample acquisition counts < 10,000 will be excluded from the analysis.

Outcomes of interests: FICD3MED; FICD3MN, FICELMED, FICELMN

May 7, 2018

a. Tables:

- Completeness of data for all measurement time points
- Summaries for each outcome at each measurement time point: N, median, 25th and 75th percentiles, min, max
- Summaries for each outcome's absolute change from baseline to each measurement time point: N, median, 25th and 75th percentiles, min, max

Wilcoxon rank sum tests will be used for the comparisons of change (from pre-dose) between groups.

b. Figure:

Longitudinal, participant-specific, (spaghetti) plots for all measurement time points using different panels/symbols/colors for RMD and placebo, separately for each cohort.

Median (change from pre-dose) plots for combined cohorts and placebo groups.

- 7.11.5 Changes in total HIV-1 DNA and 2-LTR circles in resting or total CD4+ T-cells from baseline to 6, 12, 24, and 48 hours and 7, 14, and 28 days after the administration of RMD or placebo.
- 7.11.6 Pharmacokinetic parameters (AUC, Cmax, Cmin) for RMD and co-administered antiretroviral drugs (EFV, DTG, or RAL).

Table summarizing of the pharmacologist-estimated PK parameters.

7.11.7 Number/percent of subjects with HIV-1 RNA levels > 200 copies at the Day 7 visit

See 7.7

7.11.8 All reported Grade 2-4 AEs.

List showing all the events with grade 2-4 for each study participant. The list will include the following:

- public ID
- treatment dispensation date
- visit week
- onset date
- resolution date
- event description

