7.13 Cohort 4 primary efficacy outcomes

7.13.1 Change in plasma HIV-1 RNA levels from baseline (average of pre-entry and entry values) as detected by single copy assay before and 24 hours after each administration of RMD or placebo in Cohort 4.

The analysis of 7.13.1 will be combined with 7.14.1. The available timepoints are: pre-entry (-35 to -28 days), pre- & 24hr post-infusion for all 4 infusions, and 72hr post-2nd-infusion

SCA values below the limit of detection (LOD) will be imputed as equal to half the limit of detection (i.e., if LOD=0.4 copies/mL, results < 0.4 copies/mL will be imputed as 0.2 copies/mL).

a. Tables:

- Completeness of data for all measurement time points
- N (%) of SCA value < LOD at all measurement time points
- Baseline SCA: N, median, 25th and 75th percentiles, min, max
- Pre- and 24hr post-infusion SCA for each infusion and 72hr post-2nd-infusion: N, median, 25th and 75th percentiles, min, max
- Change (at each post-entry time point baseline) SCA: N, median, 25th and 75th percentiles, min, max
- Change (post-infusion time point pre-infusion time point for each infusion) SCA: N, median, 25th and 75th percentiles, min, max

NOTE: Baseline averages will be calculated using log10-transformed SCA values.

Wilcoxon rank sum test will be used for the comparison between groups. Wilcoxon signed rank test will be used to test within-group changes for RMD group. Two-sided 95% confidence intervals for the shift will be calculated based on Hodges-Lehmann estimator.

b. Figure:

- Longitudinal median (Q1, Q3) plots for all measurement time points by RMD and placebo.
- Longitudinal, participant-specific, (spaghetti) plots for all measurement time points with open symbol for values below the LOD and different symbols/colors for RMD and placebo.

7.13.2 Change in cell-associated HIV-1 RNA levels in PBMCs before and 24 hours after each administration of RMD or placebo in Cohort 4.

The analysis of 7.13.2 will be combined with 7.14.2. The available timepoints are the same as 7.13.1 and 7.14.1. The same analysis approach will be used as in 7.13.1 (except N (%) below LOD).

NOTE: Cell-associated RNA results below the detection limit are imputed with 1 copy/million PBMCs.

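### SAP 7.14.3 analyses Cohort 4 histone acetylation by the cell-associated RNA method, which drops the assay's low-count rule, cites a baseline that cannot be averaged, and omits 3 of 12 scheduled time points from the list

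*SAP*

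**What the plan says.** SAP 7.14.3 defines the outcome as "Changes in histone acetylation in CD4+ and CD8+ T-cells from baseline to after each administration of RMD or placebo in Cohort 4" and gives the method only by cross-reference: "The same analysis approach will be used as in 7.13.2".

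Section 7.13.2 is the primary analysis of cell-associated RNA in PBMCs. It takes over the approach of 7.13.1 (plasma HIV-1 RNA by single-copy assay), apart from the count of values below the detection limit. On timing it states "The available timepoints are the same as 7.13.1 and 7.14.1". The 7.13.1 list is one pre-entry visit (days -35 to -28), then "pre- & 24hr post-infusion for all 4 infusions, and 72hr post-2nd-infusion". Section 7.13.2 adds "Cell-associated RNA results below the detection limit are imputed with 1 copy/million PBMCs".

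For the same outcome in Cohorts 1-3, SAP 7.11.4 describes a flow-cytometry measure in total CD4+ T-cells. It names four fluorescence-intensity (FI) variables, summarises absolute change from baseline, and sets a quality rule: "Mean and median FI records with sample acquisition counts < 10,000 will be excluded from the analysis". Sections 7.13.1, 7.13.2 and 7.14.3 repeat neither the rule nor the variable names.

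The Cohort 4 schedule (Protocol Tables 6.1.3-1 and 6.1.3-2; SAP Appendix 1) places histone acetylation at Hour 0, 24 h and 72 h of each infusion, and at neither pre-entry visit. Protocol 6.3.10 has the Cohort 4 assay run in real time according to that schedule.

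**The concern.** The Protocol's testing plan (Section 2.2) includes histone acetylation to show whether romidepsin acts on its target in vivo. If the virologic outcomes show no effect, this measure helps to separate a drug that did not reach its target from one that did and still failed to induce virus. Its analysis should therefore be settled before the data are seen.

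As written, the analyst inherits a method designed for RNA copy numbers. Low-count records that the SAP treats as unusable in Cohorts 1-3 would be kept in Cohort 4, the inherited baseline does not fit the sampling, and later acetylation levels (72 h) would be tabulated after one infusion of four. With 12 active and 3 placebo participants planned, a choice made at analysis about a few records or time points can change the result.

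**Working it through.** The plan gives no figure of its own here. The check compares the sampling schedule with the rules that 7.14.3 imports.

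**1. Time points.** Scheduled: 4 infusions x 3 samples = 12. The 7.13.1 list: 1 pre-entry + 4 pre-infusion + 4 at 24 h + 1 at 72 h = 10.

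| | Hour 0 | 24 h | 72 h | Total |
|---|---|---|---|---|
| Histone samples scheduled | 4 | 4 | 4 | 12 |
| Also in the 7.13.1 list | 4 | 4 | 1 | 9 |
| Not listed | 0 | 0 | 3 (infusions 1, 3, 4) | 3 |

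Unlisted: 3/12 = 25% of scheduled points. Of the 8 post-infusion points, 5 are listed and 3 (37.5%) are not. The tenth entry in the list, the pre-entry visit, has no histone sample. The level-summary bullet in 7.13.1 has the same restriction as the list.

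**2. Source of the 72 h limit.** The notes under 7.14.1 and 7.14.2 say that, of the 72 h samples, only those after infusion 2 had been tested for the primary analysis. Both notes concern RNA, and 7.14.3 carries no such note.

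**3. Baseline.** The 7.13.1 outcome uses the mean of pre-entry and entry values. Pre-entry histone samples scheduled: 0, so that mean cannot be formed for any participant. An Hour 0 sample before infusion 1 is scheduled, and a pair of Hour 0 and 24 h values can be formed for 4 of 4 infusions.

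The general definition in SAP 6.4 takes the most recent assessment up to and including Day 0, with Day 0 set at registration. Protocol 6.2.2 allows Cohort 4 entry evaluations up to 24 hours after randomization. If Hour 0 falls on the next calendar day, the literal 6.4 rule misses it. SAP 6.6 anchors study days on infusion dates, which points the other way. Naming Hour 0 removes the doubt.

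**4. Count rule and variables.** Both appear in 7.11.4 only, under a heading limited to Cohorts 1-3. Section 7.14.3 also adds CD8+ T-cells, for which no variable is named.

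**5. What the count rule could cost.** With n RMD and m placebo values and no ties, the smallest two-sided exact rank-sum p-value is 2/C(n+m, m):

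- 12 v 3: 2/455 = 0.004
- 12 v 2 (one placebo record excluded): 2/91 = 0.022
- 12 v 1 (two excluded): 2/13 = 0.15

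One lost placebo record still allows p < 0.05; two do not. This is a reason to decide in advance whether the rule applies.

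**The case against.** The strongest reply is that 7.14.3 borrows only an analysis approach. In 7.13.2 the time points and the approach are in separate sentences, so the RNA time-point list need not come with it. The outcome covers change after each administration, 7.13.1 summarises change at every time point after entry, and its plots cover every measured time point. Those phrases can be read to include all the 72 h samples. On baseline, the 7.14.3 text does not mention an average, SAP 6.4 supplies a general rule, and the change within each infusion needs no pre-entry value.

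Much of this stands, and it rules out several stronger readings. A reader might infer that no baseline exists; only the two-visit mean is unavailable. A reader might infer that the three 72 h points have no analysis; they are missing from the list and the level summary, but nothing expressly drops them from changes or plots. The 12 points are scheduled samples, and neither document reports how many were obtained. The imputation note is confined by its wording to RNA results and cannot alter a fluorescence value. A loss of comparability with Cohorts 1-3 cannot be blamed on this cross-reference, since cell types and sampling times differ anyway and no histone comparison between the two stages is planned.

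It is also true that no document shows a Cohort 4 record below 10,000 events, so the effect of the missing rule is unknown. But the reply has no answer on the rule itself: nothing in the chain from 7.14.3 to 7.13.1 contains it. On the other points it shows that a sensible analyst could repair the text, which still leaves the repair to be chosen at analysis.

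**Conclusion.** The cross-reference is a poor fit and should be replaced. Followed literally, it keeps records that the same SAP excludes for this outcome in Cohorts 1-3, invokes an average that cannot be computed, and leaves 3 of 12 scheduled points (3 of 8 post-infusion) out of the time-point list and level summary for a reason that belongs to RNA testing.

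This is a moderate point about a secondary outcome. The primary safety and efficacy analyses are unaffected, and no numerical bias can be estimated from the documents. The conclusion assumes that Cohort 4 uses the same kind of flow-cytometry measure as 7.11.4, since 7.14.3 names no platform. It also assumes that samples follow the schedule.

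The SAP already has a better model: the text shared by 7.14.8 to 7.14.11, which includes P-TEFb phosphorylation, summarises each measured time point and absolute change from baseline without borrowing from an RNA assay.

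**What to change.** Replace the cross-reference in 7.14.3 with text specific to histone acetylation:

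- Apply the 10,000-count exclusion and the FI variables of 7.11.4, naming the variables for CD4+ and for CD8+ T-cells. Protocol 6.3.10 describes the Cohort 4 assay in total CD4+ cells only, so confirm that CD8+ results are produced.
- Define baseline as the Hour 0 value of infusion 1.
- Summarise levels, absolute change from that baseline, and absolute change from the same infusion's Hour 0, at 24 h and 72 h for all four infusions. Both changes are needed: same-infusion change alone would drop the change from baseline that Protocol 9.2.2.3 specifies.
- Keep the rank-sum comparison, the signed-rank test within the RMD group and the Hodges-Lehmann interval from 7.13.1.

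The cost is a short SAP edit with no new samples or data. The one drawback is that a low-count record may be lost from a placebo group of 3, so report the number of excluded records by arm and time point.

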7.15 Cohort 4 exploratory outcomes

- 7.15.1 Change in total virus recovery (TVR) or qVOA from baseline to after administration of all doses of RMD or placebo in Cohort 4
- 7.15.2 Changes in proportion of cycling CD4+ and CD8+ T-cells (Ki67 expression) from baseline to after each administration of RMD or placebo in Cohort 4.
- 7.15.3 Changes in the levels of soluble markers IL-6, C-reactive protein (CRP), and D-dimer from baseline to after each administration of RMD or placebo in Cohort 4.
- 7.15.4 Changes in HIV-specific immune responses from baseline to after the first and fourth administration of RMD or placebo in Cohort 4.
- 7.15.5 Changes in host RNA expression profiles by RNAseq of PBMC from after the first and fourth administration of RMD or placebo in Cohort 4.

Appendices

Appendix 1Schedule of Events (protocol Section 6)

Cohort 4, Screening through Step 2

	Screenin g	Pre-Entry	Pre-Entry		ę	Step 1					Step 2			c
	Scre ç	Pre-E	Pre-E						Step 2 Reg.			_		ldy D/C
Evaluation (Cohort 4, Screening through Step 2; standard)	Day -60 to Day -36	Day -35 to Day -28	Day -14 to Day -3	Entry/ Hour 0 Pre- Infusion/Infusion	Week 1 / Day 1 (24 hr post- infusion)	Week 1/ Day 3 (72 hr post- infusion)	Week 1 / Day 7 (7 days post- infusion)	Weeks 2 to 8 (conditional) ¹	Week 2 / Day 14 (+/- 48hr)	Week 3 / Day 15 (24 hr post- infusion)	Week 3 / Day 17 (72 hr post- infusion)	Week 3 / Day 21 (7 days post- infusion)	Weeks 4 to 11 (conditional) ¹	Prem. Tx and Study
Documentation of HIV-1	Х													
Medical and Medication History	X			X										
Clinical Assessments	x	x	x	x	x	х	х	Once each week	х	х	х	x	Once each week	x
Complete Physical Exam		Х												
Targeted Physical Exam			x	x	x	х	x	Once each week	x	x	x	x	Once each week	x
Hematology			Х		X	Х	Х	Wk 2, 6		Х	X	X	Wk 6, 10	Х
Potassium and Magnesium (see section 6.3.7 for timing at Pre- entry)			x				x	Wk 2, 6				x	Wk 6, 10	
LFTs/Blood Chemistries (see section 6.3.7)				X			х	Wk 2, 6				x	Wk 6, 10	х

Page 23 of 28

	Screenin g	Pre-Entry	Pre-Entry		5	Step 1					Step 2			D/C
	Scr	Pre-	Pre-						Step 2 Reg.					
Evaluation (Cohort 4, Screening through Step 2; standard)	Day -60 to Day -36	Day -35 to Day -28	Day -14 to Day -3	Entry/ Hour 0 Pre- Infusion/Infusion	Week 1 / Day 1 (24 hr post- infusion)	Week 1/ Day 3 (72 hr post- infusion)	Week 1 / Day 7 (7 days post- infusion)	Weeks 2 to 8 (conditional) ¹	Week 2 / Day 14 (+/- 48hr)	Week 3 / Day 15 (24 hr post- infusion)	Week 3 / Day 17 (72 hr post- infusion)	Week 3 / Day 21 (7 days post- infusion)	Weeks 4 to 11 (conditional) ¹	Prem. Tx and Study
¹ These "conditional" evalu				only for par							Step. (S	ee sectio	on 6.2.3). lf
Urinalysis	X		[
Urine Pregnancy Testing	x	х	x	х					х					
HBV/HCV screening	Х													
ECG		Х		X Hr 4 As clinically indicated						As	clinically	indicate	d	
CD4%			Х	Х	Х	Х			Х	Х	Х			X
Stored Plasma and PBMC for immunology testing (see section 6.3.9)		X	x		x					x				x
Plasma HIV-1 RNA real time	x		x											Х
Plasma HIV-1 RNA expedited							х	Once each week				х	Once each week	
Plasma HIV-1 RNA by SCA		X	x	x	x	x			x	x	x			X
¹ These "conditional" evalua infusion will be delayed, go					-		sions wi	ll be del	ayed for	the next \$	Step. (Se	e sectior	n 6.2.3).	lf

	Screenin g	Pre-Entry	Pre-Entry		Ş	Step 1					Step 2			D/C
	Scre	Pre-E	Pre-E						Step 2 Reg.					
Evaluation (Cohort 4, Screening through Step 2; standard)	Day -60 to Day -36	Day -35 to Day -28	Day -14 to Day -3	Entry/ Hour 0 Pre- Infusion/Infusion	Week 1 / Day 1 (24 hr post- infusion)	Week 1/ Day 3 (72 hr post- infusion)	Week 1 / Day 7 (7 days post- infusion)	Weeks 2 to 8 (conditional) ¹	Week 2 / Day 14 (+/- 48hr)	Week 3 / Day 15 (24 hr post- infusion)	Week 3 / Day 17 (72 hr post- infusion)	Week 3 / Day 21 (7 days post- infusion)	Weeks 4 to 11 (conditional) ¹	Prem. Tx and Study
Resting CD4+ T cells (see section 6.3.10)		х	x	х	x	x			x	х	x			x
Stored PBMC for virology testing (see section 6.3.10)		x	x	x	x	x			x	x	x			x
Histone Acetylation				Hr 0	x	x			Hr 0	X	x			
Stored PBMC for TVR assay (see section 6.3.10)		x												
RMD/Placebo Infusion				Х					X					
ART Adherence Assessment	x		x	х					x					x
¹ These "conditional" evaluation infusion will be delayed, go							sions wi	ll be del	ayed for	the next s	Step. (Se	e sectior	n 6.2.3).	lf

			Step 3					St	ep 4					D/C
	Step 3 Reg.					Step 4 Reg.				st-Inf Follov		4	Study D	
Evaluation (Cohort 4, Steps 3 and 4; standard)	Week 4 / Day 28 (+/- 48hr)	Week 5 / Day 29 (24 hr post-infusion)	Week 5 / Day 31 (72 hr post-infusion)	Week 5 / Day 35 (7 days post- infusion)	Weeks 6 to 13 (conditional ¹	Week 6 / Day 42 (+/- 48hr)	Week 7 / Day 43 (24 hr post-infusion)	Week 7 / Day 45 (72 hr post-infusion)	Week 7 / Day 49 (7 days post- infusion)	Week 8 / Day 56	Week 11 (±3 days)	Week 16 (± 7 days)	Week 24 (± 7 days)	Prem. Tx and/or S
Clinical Assessments	х	х	x	x	Once each week	х	x	х	x	Х	x	x	x	x
Targeted Physical Exam	Х	Х	Х	Х	Х	Х	Х	Х	Х	Х	Х	Х	Х	Χ
Hematology		X	X	X	Wk 8, 12		x	X		Х	Х	X	Х	X
Potassium and Magnesium (see section 6.3.7 for timing at Pre- entry)				x	Wk 8, 12				x					
LFTs/Blood Chemistries (see section 6.3.7)				x	Wk 8, 12				x				X	x
Urine Pregnancy Testing	X					x					s clin indic		/	
ECG	х	As	clinically	indicated	l	X Hr 4	As clir	nically indi	cated	х				
¹ These "conditional" eval If infusion will be delayed							ns will be d	lelayed for	the next s	Step.	(See :	sectio	on 6.2	2.3).
CD4%	X	X	X			X	X	X		Х	X	X	Х	X

			Step 3					Ste	ep 4					D/C
	Step 3 Reg.					Step 4 Reg.			Ро	4				
Evaluation (Cohort 4, Steps 3 and 4; standard)	Week 4 / Day 28 (+/- 48hr)	Week 5 / Day 29 (24 hr post-infusion)	Week 5 / Day 31 (72 hr post-infusion)	Week 5 / Day 35 (7 days post- infusion)	Weeks 6 to 13 (conditional ¹	Week 6 / Day 42 (+/- 48hr)	Week 7 / Day 43 (24 hr post-infusion)	Week 7 / Day 45 (72 hr post-infusion)	Week 7 / Day 49 (7 days post- infusion)	Week 8 / Day 56	Week 11 (±3 days)	Week 16 (± 7 days)	Week 24 (± 7 days)	Prem. Tx and/or Study
Stored Plasma and PBMC for immunology testing (see section 6.3.9)		x					x			х	x	x	x	x
Plasma HIV-1 RNA real time									X	Х		х		x
Plasma HIV-1 RNA expedited				х	Once each week						x			
Plasma HIV-1 RNA by SCA	x	x	x			x	x	x		x	x	x	х	x
Resting CD4+ T cells (see section 6.3.10)	x	x	x			x	x	x		х	x	х	x	x
Stored PBMC for virology testing (see section 6.3.10)	x	x	x			x	x	x		x	x	x	x	x
Histone Acetylation	Hr 0	x	x			Hr 0	x	x						
¹ These "conditional" eva If infusion will be delayed							ns will be d	lelayed for	the next s	Step.	(See :	sectio	on 6.2	.3).
Stored PBMC for TVR (see section 6.3.10)				,							x		X	
RMD/Placebo Infusion	X					X								

			Step 3					Ste	ep 4					D/C
:	tep 3 eg.					Step 4 Reg.				st-Infi Follov		4	Study D	
Evaluation (Cohort 4, Steps 3 and 4; standard)	48hr)	Week 5 / Day 29 (24 hr post-infusion)	Week 5 / Day 31 (72 hr post-infusion)	Week 5 / Day 35 (7 days post- infusion)	Weeks 6 to 13 (conditional ¹	Week 6 / Day 42 (+/- 48hr)	Week 7 / Day 43 (24 hr post-infusion)	Week 7 / Day 45 (72 hr post-infusion)	Week 7 / Day 49 (7 days post- infusion)	Week 8 / Day 56	Week 11 (±3 days)	Week 16 (± 7 days)	Week 24 (± 7 days)	Prem. Tx and/or S
ART Adherence Assessment	x					x						X	x	X
PK RMD 2	X					Х								
(Collection times are H	lr O					Hr 0								
from the start of the	&					&								
infusion) H	lr 4					Hr 4								
PK ARVs 2	X					Х								
•	lr 0	X				Hr 0	X							
the start of the infusion)							s will be d
